2.2 Clinical Hypotheses

BOTOX injected bilaterally into the bulbospongiosus muscle has an acceptable safety profile and shows an efficacy signal in comparison to placebo, as demonstrated by an increased IELT.

3. Study Design

This is a phase 2a, multicenter, randomized, double-blind, placebo-controlled, single treatment, pilot study followed by an open-label observation period, to assess a range of BOTOX doses for the treatment of male patients with PE. Patients will attend a minimum of 6 or 7 clinic visits and also have 1 or 2 telephone visits in the randomized period: screening, day 1 (treatment), day 2 (telephone visit for non-sentinel patients, clinic visit for sentinel patients, week 1 (telephone visit, and weeks 2, 4, 8, and 12/study exit). Partners will need to either attend a clinic visit or participate on a video conference during the screening period to provide informed consent and to receive training on measurement and recording of the IELT. For the open-label period, patients will have 2 clinic visits (weeks 4 and 12/study exit), along with 3 telephone visits (day 2, weeks 2, and 8).

For Cohorts 1-5, patients will be enrolled in cohorts of 10 patients. Within each cohort, 8 patients will receive BOTOX and 2 patients will receive placebo. For Cohort 6, patients will be enrolled into the randomized period in a 1:1 ratio, with 12 patients receiving BOTOX and 12 patients receiving placebo. Cohort 6 patients may choose to participate in the open-label period where they will receive BOTOX. For each treatment, patients will receive one injection of study medication delivered by ultrasound guidance bilaterally to the bulbospongiosus muscle.

Table 3–1 shows the planned dose escalation scheme; although, other interim doses may be recommended for investigation by the independent Data Review Committee (DRC) following data review.

Cohort	Total Dose	Sample Size	Total Patients in Cohort
1		N = 8	10
1	Placebo	N=2	10
2		N = 8	10
2	Placebo	N = 2	10
3		N = 8	10
	Placebo	N = 2	10
4		N = 8	10
	Placebo	N = 2	10
5		N = 8	10
	Placebo	N=2	10
6		N = 12	24
	Placebo	N = 12	24

Table 3–1 Planned Dose Escalation Scheme

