5.4 Treatment Allocation Ratio and Stratification

Patients will be randomly allocated (based on a randomization schedule, prepared by Allergan biostatistics) to BOTOX or placebo.

Study medication allocation will be performed using the interactive voice response system (IVRS) or the interactive web response system (IWRS).

For Cohorts 1-5, the allocation ratio for sentinel patients will be 1:1 BOTOX to placebo. The allocation ratio for subsequent patients will be 7:1 BOTOX to placebo. Two additional sentinel patients can be enrolled if requested by the DRC; further sentinel patients will be treated with BOTOX and will be in addition to the 10 planned patients within a cohort.

For Cohort 6, no sentinel dosing will occur. Twenty-four patients will be randomized at a ratio of 1:1 to receive either BOTOX or placebo. Patients who choose to participate in the open-label period will receive treatment with BOTOX.

There will be no stratification performed in the study.

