2.3 Data Conventions

- A one-sided, alpha=0.1 significance level will be used for this study for treatment comparisons, i.e., treatment differences are considered significant if the 1-sided p-value of the test used in the comparison is less than or equal to 0.1.
- Data will be pooled across centers in all analyses. Placebo patients from different cohorts will also be pooled to form the placebo treatment group in all analyses.
- Day 1 is defined as the day of the first study medication administration. Study day is calculated as: Study day=visit date-day 1 date +1 for visits occurred after day 1 and study=visit date -day 1 date for visits occurred before day 1.
- The Medical Dictionary for Regulatory Activities (MedDRA) will be used to code all adverse events and medical history.
- Medications will be coded by the World Health Organization Drug Dictionary Enhanced (WHO DDE) preferred name for the medication's name and MedDRA for the medication's indication.
- All adverse events/medications with missing onset/stop dates will be identified and the missing dates will be imputed as follows:
 - a) For adverse event onset date: if day and month are missing but year is available then the imputed date would be January 1st of that year, or day 1 if they are in the same year. If day is missing but month and year are available then the imputed day will be the first day of the month or day 1 if they are in the same month and year.
 - b) For adverse event stop date: if day and month are missing but year is available then the imputed day will be December 31st of that year, or the study exit date if they are in the same year. If only day is missing but moth and year are available then the imputed day will be the last day of the month of the year, or the study exit date if they are in the same month and year.

- Data from unscheduled/re-test visits, excluding lab data, will also be treated the same way as scheduled visits, i.e., put in the visit window and decided by the visit day's distance to target day as which one to be used in the analyses.
- Weight and height will be presented with the metric system units and laboratory data will be presented with the Standard International (SI) units.
- Summary statistics for continuous/ordinal data include sample size (N), mean, standard deviation, minimum, median, and maximum and that for categorical data include sample size (N), frequency count and percentage.

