6.4 Adverse Events

AEs will be coded from the verbatim text into PT and the primary SOC using MedDRA.

AEs are collected both for the screening/baseline period pretreatment (which are referred to as pretreatment AEs) and for the follow-up period after treatment is initiated (which are referred to as posttreatment AEs). A treatment-emergent adverse event (TEAE) is an adverse event with onset on or after the initiation of study treatment or an adverse event with onset prior to study treatment that worsened in severity or became serious after the initiation of study treatment. For the randomized period of the study, TEAEs are those with onset on or after the first study treatment, and prior to the study treatment for the open-label period, if applicable; for the open-label period, TEAEs are those with onset on or after the study treatment for the open-label period.

Three incidence rate tables are standard for summarizing all TEAEs:

- by descending order of incidence rate
- by primary SOC and PT
- by primary SOC, PT and severity

Number and percent of patients with TEAEs will be tabulated by relationship to study drug and study procedures. All treatment-related TEAEs, either study drug-related or study procedure-related will also be presented by descending incidence and by primary SOC and PT for each treatment group. Separate tables will be generated for study drug-related and study procedure-related TEAEs. TEAEs leading to study discontinuation will also be tabulated by primary SOC and PT for each treatment group.

No statistical comparisons will be made for any adverse event table.

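### Partial AE onset dates are imputed with reference to the first injection only, so some events that began after the open-label injection are counted in the randomized period (minor)

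*SAP*

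**What the plan says.** SAP 2.3 gives two rules for an incomplete AE onset date. If day and month are missing, "the imputed date would be January 1st of that year, or day 1 if they are in the same year". If only the day is missing, "the imputed day will be the first day of the month or day 1 if they are in the same month and year". The same section fixes the reference point: "Day 1 is defined as the day of the first study medication administration". It has no clause for the date of the open-label injection.

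SAP 6.4 then splits the TEAEs by onset date. For the randomized period, "TEAEs are those with onset on or after the first study treatment, and prior to the study treatment for the open-label period". The open-label rule reads: "for the open-label period, TEAEs are those with onset on or after the study treatment for the open-label period".

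The Protocol makes the split matter. Cohort 6 is randomized 1:1, "with 12 patients receiving BOTOX and 12 patients receiving placebo" (Section 3, Study Design). In the second period everyone gets active drug: "Patients who choose to participate in the open-label period will receive treatment with BOTOX" (Section 5.4). Section 3.3 requires at least 12 weeks between the two injections and allows open-label Day 1 up to 4 weeks after the week-12 visit. SAP 2.3 pools placebo patients from all cohorts.

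**The concern.** At the first injection the rule is protective. An onset that could lie on either side of Day 1 within the same month or year is set to Day 1, so it counts as treatment-emergent. No such protection exists at the second injection. An onset that could lie on either side of the open-label injection goes to the start of the month or year, or back to the first injection, and all of these normally precede the second injection.

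SAP 6.4 has been adapted to two treatment periods, while the current text of 2.3 still knows only one injection.

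At stake is the period, and for placebo-randomized patients also the treatment, under which an AE is shown. A moved event leaves the open-label BOTOX table and enters the placebo column, so both tables understate harm on BOTOX. In a BOTOX-randomized patient the drug is the same in both periods, but the time from injection to onset is wrong. SAP 6.4.1 uses time to onset and re-challenge information when it evaluates possible distant spread of toxin. AE tables carry no tests, so the reader relies on the counts.

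**Working it through.** The documents state no figure on this point, so there is none to reproduce. The check applies the two SAP sections in sequence.

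**Inputs**
- Onset imputation and meaning of Day 1: SAP 2.3.
- Period windows: SAP 6.4.
- Gap between injections: at least 84 days, and about 84 + 28 = 112 days at the latest (Protocol 3.3).
- Planned pooled placebo: 5 cohorts × 2 + 12 = 22 (Protocol Table 3–1, pooling in SAP 2.3).

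**Step 1: logic.** With 84 days or more between injections, the first-injection Day 1 never shares a calendar month with the open-label injection.
- *Day missing, month is that of the open-label injection.* The imputed onset is the 1st of the month. This precedes the injection unless the injection was itself on the 1st.
- *Only the year known, year is that of the open-label injection.* The imputed onset is the first-injection date if that fell in the same year, otherwise 1 January. Both precede the open-label injection, unless it was itself on 1 January.

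**Step 2: invented examples, 84-day gap**

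| First injection | Open-label injection | True onset | Imputed, day missing | Imputed, year only |
|---|---|---|---|---|
| 1 Mar 2017 | 24 May 2017 | 30 May 2017 | 1 May 2017 | 1 Mar 2017 |
| 20 Oct 2016 | 12 Jan 2017 | 20 Jan 2017 | 1 Jan 2017 | 1 Jan 2017 |

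All four imputed dates fall in the randomized period. In the first row, 1 May is 23 days before the injection that the event followed.

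**Step 3: what is assigned correctly**
- First row, true onset 3 June with the day missing: imputed 1 June, stays open-label.
- First row, true onset 10 May with the day missing: imputed 1 May, correctly randomized. For injection day d = 2 to 30 of a 30-day month and onset uniform over that month, the share truly before the injection is (d − 1)/30. Its average is 15/30 = 50%.
- A year-only date in a calendar year after that of the open-label injection becomes 1 January of that later year, correctly open-label.

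**Step 4: share of partially dated open-label events moved back.** This takes first injections on each of 365 days of one calendar year, and assumes onset uniform over the stated time after the open-label injection. Share = events with imputed onset before that injection ÷ all events.

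| True onset within | Day missing | Year only |
|---|---|---|
| 7 days | 86.8% | 98.9% |
| 14 days | 75.3% | 97.9% |
| 28 days | 52.3% | 96.0% |
| 84 days | 17.5% | 88.4% |

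The shares are the same for gaps of 84 and 112 days. No randomized-period event moves forward (0%), so the error runs one way. The denominators contain only events with partial dates, not all AEs.

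**Step 5: effect of one event.** In a placebo-randomized patient with no other randomized-period TEAE, planned pooled placebo incidence rises by 1/22 = 4.5 points. In the Cohort 6 placebo arm alone the rise is 1/12 = 8.3 points. If the patient already has a randomized-period TEAE, overall incidence does not change and only the count for the specific term can.

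**The case against.** The strongest case against is that exposure is small. Only Cohort 6 patients who choose the open-label period are affected: at most 24, of whom at most 12 were on placebo. Patients are asked about AEs at every visit (Protocol 9.1.1), open-label contacts fall on day 2 and at weeks 2, 4, 8 and 12, and AEs are recorded again on open-label Day 1 when it is separate from the week-12 visit (Protocol 3.3). Onsets with an unknown month should be rare. No AE table is tested, and serious events and possible distant-spread events are also listed individually (SAP 6.4, 6.4.1, 6.5). All of this stands, and it limits the importance of the point.

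A reader might infer that every missing-day event in the month of the open-label injection is misassigned. The rule does not do that: events that truly began earlier in that month stay where they belong. A reader might also infer a breach of a stated principle that imputation must favour attribution to treatment. Neither document states one. Which way to err when a date fits both periods is a choice, but the plan should make it explicitly.

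SAP 3.3 and 5.3 do speak of day 1 of the open-label period, but with that qualifier. SAP 2.3 defines the unqualified term as the first administration. Reading Day 1 separately for each period would not settle which one applies when a partial date fits both. The part of the TEAE definition on worsening does not help either, because the open-label rule rests on onset.

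**Conclusion.** The gap is real and one-directional, but narrow. As written, SAP 2.3 and 6.4 together count an event that truly began after the open-label injection in the randomized period in two situations: day missing with onset in that injection's month (injection not on the 1st), and year only in that injection's year. In a placebo-randomized patient this shows an event on BOTOX as a placebo event, worth up to 4.5 points of planned pooled placebo incidence.

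The 4.5 points assume the planned 22 placebo patients and no other randomized-period TEAE in that patient. The shares in the working assume uniform onset and injections spread evenly over a year. The number of partial dates is unknown and probably small, so the documents do not support a claim that the safety comparison is materially distorted. The point is minor and worth closing before database lock.

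**What to change.** Add a rule to SAP 2.3 for patients treated in the open-label period:

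1. Settle the period first from the visit at which the AE was first reported. An AE already recorded at or before open-label Day 1, before the injection, stays in the randomized period.
2. Use the stop date as well. If its recorded part shows that the event ended before the open-label injection, it stays in the randomized period. Use the recorded part only, because SAP 2.3 imputes partial stop dates late.
3. Only if the period is still ambiguous, and the partial onset date is compatible with onset on or after the open-label injection, impute the open-label injection date.
4. Flag events whose period was settled by imputation in the AE listings.

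Step 3 should not be used alone. If every partial date in the month or year of the open-label injection were moved to that injection, the backward error would fall to 0%. But 17.5% (day missing) or 88.4% (year only) of partially dated randomized-period events would move forward at an 84-day gap, and 13.1% or 84.5% at 112 days, again with uniform onset.

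The cost is a few sentences in SAP 2.3 and some programming. The documents do not say whether the AE eCRF page holds the visit of first report. If it does not, the visit must be derived from source records, which under Protocol 10.4.1 include visit dates and AE status. The remaining downside is that a few true randomized-period events whose period stays ambiguous may move to the open-label table. The flag makes these visible.

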3.1 Screening Log Data

The number and percent of patients who are screen failures as well as who qualified, along with the reasons for failure, will be tabulated. The demographic information (age, race and sex) of the failed and qualified patients will be summarized. A by-site listing of the screen failures with failure reasons will be also provided.

3.2 Disposition and Exit Status

For each analysis population (safety, mITT and PP), patient disposition (enrolled, completed, discontinued, and reasons for discontinuation) will be presented by treatment group. A cumulative frequency table showing patient disposition (continuing, completed, discontinued and reasons for discontinuation) will be provided for the mITT population by visit. A by-patient data listing presenting exclusions from the PP analyses and the primary reason(s) for exclusion will be provided.

The exit status of the patients is classified as completed or discontinued. The reason for discontinuation include adverse event, lack of efficacy, lost to follow-up, personal reasons, protocol violation and other. A listing of discontinued patients with exit reasons will be provided.

Enrollment by site will be tabulated with the number and percent of patients screened, randomized, treated, completed and discontinued.

The summaries will be provided for both the randomized period and for the open-label period of the study, where applicable.

3.3 Study Duration

The length of study duration for each subject is defined as the duration between the baseline and exit dates. Summary statistics of study duration by treatment will be provided for the randomized period, the open-label period and the whole study period (including the randomized period and the open-label period). Duration for the open-label period starts from the treatment day (day 1) of the open-label period.

3.4 Protocol Deviations

Significant protocol deviations will be summarized with incidence by deviation type broken further by whether deviation leads to data exclusion from per protocol analysis for both the randomized period and the open-label period.

4. Demographics and Other Baseline Characteristics

Unless otherwise specified, summaries planned in this section will be presented using the mITT population, for patents who participated in the randomized period and for those who participated in the open-label period. If a subject participates in the open-label period, the demographics and baseline characteristics for the open-label period use the same values as those for the randomized period. For summaries for the open-label period, comparisons will not be performed.

4.1 Demographics

Age, race, sex are collected in the demographics Case Report Form (CRF) and height and weight are collected as part of the pre-treatment vital signs. All will be summarized using frequency table and/or summary statistics, both by treatment group and overall. Age will be further categorized into <35 and \geq 35 years of age groups. Race will be summarized as Caucasian, Black, Asian, Hispanic and other, as well as Caucasian vs. non-Caucasian (Black, Asian, Hispanic and other combined).

Patients' age, weight and height will be analyzed using a one-way ANOVA to evaluate any baseline differences among the treatment groups. The distributions of race (Caucasian and

non-Caucasian) will be compared among the treatment groups using Pearson's Chi-square test or Fisher's exact test. A patient level listing will be provided for all demographic data, including height and weight.

4.2 Disease Characteristics

Baseline disease characteristics include baseline IELT,

Summary statistics will be provided for each variable by treatment group as well as overall. An one-way ANOVA will be used to compare these characteristics among treatment groups. For IELT, as the eligibility is based on the average of the latest four eligible events collected at during screening period, arithmetic mean will be used.

4.3 **Prior Medications**

Prior medications are medications captured in the CRF that are taken prior to the day 1. A medication is a prior medication if the (imputed) onset date is before day 1. The number and percent of patients who had taken prior medications will be presented for each treatment group and overall by the WHO DDE preferred name and the MedDRA preferred term (PT) of the medication's indication.

4.4 Concomitant Medications/Procedures

Concomitant medications are medications taken on or after the day of study medication administration. A medication is a concomitant medication if the (imputed) onset date is on or after day 1, or if the onset date is before day 1 and the stop date is after day 1 (discontinued after day 1 or ongoing during the study).

The number and percent of patients who had taken concomitant medications will be presented for each treatment group and overall by the WHO DDE preferred name and the MedDRA PT of the medication's indication.

4.5 Past Medical History

Medical history with onset dates prior to the informed consent date will be tabulated and presented for each treatment group and overall. Medical history will be coded using MedDRA primary system organ class (SOC). All medical history will be presented by

treatment group and overall. No statistical comparisons will be performed. A patient-level listing of medical and surgical histories will also be provided for each treatment group.

Patients are also asked to fill out a sexual history CRF which will record their PE therapy or techniques together with start/stop date information. The un-coded therapy/technique will be tabulated with number and percent of patients using each therapy/technique by treatment group and overall. A patient-level listing of the information collected will also be presented.

5. Efficacy Analyses

5.1 Collection of Primary Efficacy Measurement(s) and Derivation of Primary Efficacy Variable(s)

The primary efficacy measurement is the patient's IELT (second) collected from the Sex Intercourse Diary (SID). The SID will be completed by the patient and/or their female partner after any vaginal sexual activity during the screening visit and for 12 or 24 weeks following study treatment. Only IELTs from evaluable events recorded in the SID will be used for analyses.

An evaluable event is defined as:

• An event in which the patient and his partner had vaginal intercourse, and the couple have recorded that the ejaculation occurred "intravaginally" and duration of the time from penetration to ejaculation has been recorded

OR

• An event in which the patient and his partner attempted to have vaginal intercourse. However, the couple have recorded that ejaculation occurred "prior to vaginal penetration". In this scenario, the duration of time will be recorded as zero.

Any other scenarios will not be considered as evaluable and will not be included in deriving the primary efficacy variable, although time to withdrawal can be used in exploratory analyses. Number of evaluable events will be summarized by treatment group at baseline, weeks 2, 4, 8 and 12 for the randomized period of the study.

The primary efficacy variable is the change from baseline in logarithm value of the individual patient's geometric mean IELT for the entire 12 weeks of the randomized period of the study.

For baseline, the geometric mean IELT is calculated from the most 4 recent evaluable events prior to study medication administration. The geometric mean of the IELTs from all postbaseline evaluable events up to week 12 is then calculated and the difference in the logarithm of the two geometric mean IELTs (postbaseline - baseline) will be calculated.

For IELTs that are zero (events in which ejaculation occurred prior to vaginal penetration), 0.5 (second) will be added for the calculation of geometric means.

